4.1 Registration with the Masonic Cancer Center Clinical Trials Office

Any patient who has been consented is to be registered in OnCore by the Primary Clinical Research Coordinator (PCRC) or designee. If a patient is consented, but not enrolled, the patient's record is updated in OnCore as a screen failure and reason for exclusion recorded.

4.2 Study Enrollment with the Masonic Cancer Center Clinical Trials Office

To be eligible for study enrollment, the patient must sign the research consent and meet each of the inclusion criteria and none of the exclusion on the eligibility checklist (Appendix I) based on the eligibility assessment documented in the patient's medical record.

The Primary Clinical Research Coordinator (PCRC) or designee will add the "on-treatment" date to complete enrollment.

5 Study Plan

Patients enrolled in this study receive standard of care (RE therapy but agree to serial sample collections for research purposes as detailed in Section 7.

Direct study participation ends after the final blood sample is collected 12 weeks after the RE therapy unless any of the following occurs:

- The patient is non-compliant or withdraws consent
- The patient is discharged to hospice for terminal cancer care

As part of the consent process, the participant will be asked to opt in to the storage of any leftover blood or tumor samples for future unspecified research once testing related to this study is completed and verified.

6 Expected Adverse Events and Potential Risks

6.1 Risks of Blood Sample Collection

The risk of blood sample collection is very minimal and include infection and hematoma.

6.2 Risks of Hepatic Tumor Biopsy

Risks of hepatic tumor biopsy include significant hemorrhage, requiring transfusion or secondary procedure, infection, track seeding, or accidental damage to surrounding structures. However, the risks for each of these complications is ≤ 1%.

7 Study Calendar/Schedule of Tests and Procedures

7.1 Required Clinical Care Evaluations

	Screening	
	within 28 days of enrollment	within 14 days of enrollment
Written Consent	X	
Medical history	X	
Confirmation of hepatic metastases meeting study eligibility requirements	X	
Provider assessment for eligibility	X	
ECOG performance status	X	
Complete Blood Count with diff (CBC), INR		X
Total bilirubin		X
Pregnancy test (urine or serum) WOCBP		X ¹

¹For women of childbearing potential (WOCBP): urine pregnancy test within 14 days prior to study registration. If a urine test is positive or cannot be confirmed as negative, a serum pregnancy test will be required.

Medical History: This will be obtained during the standard of care pre-RE clinical visit with the treating interventional radiology. The Interventional radiologist will collect the information directly from the patient. At this time ECOG status will also be determined by the interventional radiologist

Laboratory values: The laboratory values (CBC, INR, total bilirubin, and Pregnancy test) will be gathered from Epic, as this testing is standard of care prior to RE.

7.2 Research Related Sample Collection

	Prior to RE	Time post RE			
		1 week (± 6 days)	2 weeks (±7 days) optional	4 weeks (± 2 weeks)	12 weeks (± 2 weeks)
Assess for adverse events		X	X	X	X
Peripheral blood for cytokines	X	X		X	X
Peripheral blood for lymphocytes	X	X		X	X
Tumor biopsy	X		X a treated and an untreated tumor		

Research sample collection will be tied to the clinical care time points whenever possible. It is recognized that with novel therapies as used in this study, the timing of protocol directed research samples may miss important patient specific events. For this reason, up to 3 extra samples for a total of 180 ml of blood may be drawn at additional time points that are not specified above. This blood would be drawn in the case that blood draws from specified time points were damaged, lost, or unusable.

7.3 Endpoints, detailed:

The primary endpoint for this study is to determine changes in the peripheral blood monocytes after RE therapy for primary and secondary malignancies of the liver at 12 weeks.

Secondary endpoints include the changes in peripheral blood monocytes at 7 days and 4 weeks. The changes in immunologically relevant cytokines (*IL-1 α , IL-1 β , IL-2, IL-6, IL-10, IL-12p70, IL-18, TNF α , IFN- γ , Fit ligand 3, and MCP-1*) at 7 days, 4 weeks, and 12 weeks will also be determined. Biopsies of the treated tumor prior to treatment and 2 weeks after treatment (if done) will also be performed to assess immune cell infiltration following treatment. The 2-week after treatment biopsy will be performed strictly for research purposes and will be optional. The second biopsy was made optional as it was found to be a significant barrier to enrollment. Furthermore, the change in PBMCs is the most scientifically important aspect of the study. Additionally, when available, a non-treated tumor will be biopsied two weeks after treatment to assess for immune cell infiltration.

7.4 Research data collection and lab analyses detailed:

Basic characteristics of the malignancy (type of malignancy, size of largest tumor, and number of tumors) will be recorded. RE will be completed in a manner which has been previously described (20). All of the preprocedural work up and procedure costs will be billed to insurance as this is standard of care.

Clinical follow up with magnetic resonance imaging (MRI) or CT will occur at 1 month and 3 months. Radiologic response will be evaluated at 3 months using Response Evaluation Criteria in Solid Tumors (RECIST) and modified RECIST guidelines. Overall survival will be defined as time from RE to death, and patients will be censored for transplantation. Progression free survival will be defined as time from RE to progression as defined by RECIST and mRECIST.

Peripheral blood monocytes will be collected and processed for flow cytometric analyses and cryostorage for later batch studies. The effect RE on lymphocyte repertoire, numbers and phenotype will be assessed at baseline and at defined time points during the trial (7 days (+/- 6 days), 4 weeks (+/- 2 weeks), and 12 weeks (+/- 2 weeks). The frequency and percentage of peripheral blood monocytes and T-cell subsets (CD4 and CD8 effector memory, central memory and Treg subsets), NK cells and myeloid-derived suppressor cells will be determined. Peripheral blood tumor-specific T cell subsets will be evaluated by flow cytometry in cooperation with the Translational Therapy Laboratory, Masonic Cancer Center. Cytotoxic T lymphocytes (CD8+ T cells) and CD4+ helper T cells will be isolated using fluorescence-activated cell sorting (FACS) from cryopreserved cells followed by mRNA expression analysis to assess gene expression changes resulting from therapy. Testing will be performed in the UMN Flow Cytometry and Genomics Core Laboratories. Peripheral blood monocytes may also be tested in functional assays (i.e. IFN- γ ELISpot) for responses to known antigens as well as to predicted neoantigens from whole-exome/transcriptome sequencing of melanoma tumors. All patients will also undergo HLA testing to enable epitope discovery using available MHC binding prediction algorithms.

Patients will undergo biopsy of the largest percutaneous available tumor to be treated within a 12-week period prior to treatment and optionally at 2 weeks (\pm 7 days) following RE. If the pre-treatment biopsy is not standard of care, it will be done for research. The 2-week after treatment biopsy will be performed strictly for research purposes. The optional post RE biopsy will include a treated (defined as a lesion which had y90 delivered to it as determined on standard of care Bremsstrahlung scan after RE) and non-treated lesion (defined as a lesion which did not receive y90 as determined on standard of care Bremsstrahlung scan after RE). Four 18-gauge core needle biopsies will then be obtained. One of the four cores will immediately be placed on ice and sent to our CLIA approved research laboratory. This sample will then be flash frozen and

stored at -80 degrees. Three of the cores will immediately be placed into formalin and submitted to the research laboratory where they will undergo paraffin embedding. These samples will also be stored until analysis can be undertaken. A paraffin embedded sample will then undergo immunohistochemistry analysis. The samples will be analyzed using a standard streptavidin biotinylated alkaline phosphatase method or a streptavidin biotinylated horseradish peroxidase method as described previously (17,18). The slides will then be analyzed using a standard light microscope and CCD-camera at 20x objective. The slides will be scanned into digital format using an Aperio XT scanner (Leica Biosystems Inc. Buffalo Grove, IL). A pathologist will then demarcate the tumor area on the slide. This area of interest will be analyzed using the counting software "FiJI-ImageJ" (FIJI) will be used to quantify the number of infiltrating cells (cell/mm²) in the tumor. They will also be analyzed by the number of infiltrating cells per 100 tumor cells. These analytic standards have been previously described (17,18). The infiltration of immune cells into the tumor before and after treatment will then be compared with each patient serving as their own control.

On the day of RE patients will have labs drawn, as is consistent with current practice. In addition to standard labs (total bilirubin, international normalized ratio (INR), complete blood count (CBC)) the patients will have an additional tube drawn to be analyzed for cytokine level. To determine the effects on cytokines (*IL-1 α , IL-1 β , IL-2, IL-6, IL-10, IL-12p70, IL-18, TNF α , IFN- γ , Fit ligand 3, and MCP-1*) over a period of time the cytokines will be analyzed following RE at 7 days (+/- 6 days), 4 weeks (+/- 2 weeks) and 12 weeks (+/- 2 weeks). All cytokines will be measured in a similar way through the Cytokine Reference Laboratory at the UMN. This Clinical Laboratory Improvement Amendments (CLIA) approved lab specializes in the analysis of cytokines, chemokines, and growth factors, and as such is very qualified to perform these tests which they have been performing for several years on a regular basis. The tests will be performed in a similar fashion to prior authors (15-17).

The blood cells, blood serum and the biopsy samples will then be stored at the clinical research lab at the University of Minnesota

8 Event Monitoring, Documentation, and Reporting

Toxicity and adverse events will be classified and graded according to NCI's Common Terminology Criteria for Adverse Events version 5.0 (CTCAE V5) and reported on the schedule below. A copy of the CTCAE can be downloaded from the CTEP home page. (http://ctep.cancer.gov/protocolDevelopment/electronic_applications/ctc.htm#ctc_50).

The following definitions of adverse events (AEs) and serious adverse events (SAEs) will determine whether the event requires expedited reporting via the SAE Report Form in addition to routine documentation in the OnCore AE case report form (CRF).

Note: throughout this section the generic term "study drug" refers to the study related procedures.

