1.2 Secondary Objectives

- Determine changes in the peripheral blood cytokine after REtherapy for primary and secondary malignancies of the liver.
- Determine the changes in infiltrating immune cell within the treated tumor which occur after RE therapy for primary and secondary malignancies of the liver.
- Determine the changes in infiltrating immune cell within non-treated liver tumors which occur after RE therapy for primary and secondary malignancies of the liver.

2 Background and Rationale

The importance of the immune system in the treatment of cancer has been well established over the last several decades, leading to the development of immunotherapies (1). It has also been noted that certain loco-regional therapies such as external beam radiation (XRT) and thermal ablation induce immunologic responses (2-6). However, to date basic research into the immune response induced by RE, a recently established standard of care treatment for primary and secondary malignancies of the liver, is lacking (7,8).

Rarely, loco-regional therapy can induce a positive immune response systemically, termed an abscopal effect. Pre-clinical studies with XRT have suggested that single high dose radiation, not clinically obtainable with XRT, but regularly performed in RE, make abscopal events more frequent (9-11). This suggest RE may be an excellent method of inducing abscopal effects as the deliverable dose to the tumor can be as high as 200-300 Gy, much higher than clinically obtainable by XRT (11). However, despite the apparent potential of RE to positively modulate the immune system and the dramatic benefits this may provide, little research has been performed in this area.

Five prior papers have investigated cytokine changes following RE (12-16). Both Carpizo et al and Lewandowski et al focused on the release of angiogenic factors which have been shown to be tumor protecting, however, are not focused on immunomodulation.

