9.4 Record Retention

The investigator will retain study records including source data, copies of case report form, consent forms, HIPAA authorizations, and all study correspondence in a secured facility for at least 6 years after the study file is closed with the IRB.

10 Statistical Considerations

Descriptive statistics will be calculated for outcomes and variables of interest. Continuous variables will be summarized using mean and standard deviation, or median and interquartile range, as appropriate. Categorical variables will be summarized using frequencies and percentages. Plots of each peripheral lymphocyte at baseline and each subsequent time of measurement (as stated in the protocol synopsis section) will be generated. This will help determine if individuals have different baseline peripheral lymphocyte values or different peripheral lymphocyte value trends over time. Similar plots will be generated for each cytokine (*IL-1 α* , *IL-1 β* , *IL-2*, *IL-6*, *IL-10*, *IL-12p70*, *IL-18*, *TNF α* , *IFN-Y*, *Fit ligand 3*, and *MCP-1*).

Primary analysis: To determine if there is a change in peripheral lymphocytes following RE, a mixed model with random intercept and random slope for time, and adjustment for baseline peripheral lymphocyte value will be carried out for each lymphocyte. The fixed effect for time, representing the slope over time, will be tested for significance, and a 95% confidence interval will be reported. Depending on if the outcome is skewed, appropriate transformations will be used. Similar models may be carried out with adjustment for certain variables such as age, sex, and size of tumor. Additionally, to investigate specific changes in peripheral lymphocytes from baseline, pairwise comparisons between baseline and each measurement following RE, using paired t-tests or Wilcoxon signed-rank tests, will be performed with a Bonferroni adjustment for multiple comparisons.

Secondary analysis: To determine if there is a change in active cell infiltration into tumors following RE, paired t-tests or nonparametric Wilcoxon signed-rank tests will be used, depending on the distribution of the outcome. These analyses will be performed for the different tumor types (treated and non-treated tumors). In the case that certain variables such as age, sex and size of tumor are of interest, a mixed model will be obtained using an appropriate distribution assumption of the outcome (e.g. Gaussian, Poisson or negative binomial).

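### Section 10 plans a paired before/after test in non-treated tumours, but Sections 7.3 and 7.4 schedule their biopsy only after radioembolization

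*Combined protocol and SAP*

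**What the plan says.** **Objective.** Section 1.2 sets out to "Determine the changes in infiltrating immune cell within non-treated liver tumors which occur after RE therapy". The synopsis lists the same objective in nearly the same words.

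**Analysis.** For change in infiltration after RE, the secondary analysis in Section 10 says "paired t-tests or nonparametric Wilcoxon signed-rank tests will be used, depending on the distribution of the outcome". It then adds: "These analyses will be performed for the different tumor types (treated and non-treated tumors").

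**Sampling in the detailed sections.** Section 7.3 gives the treated tumour a biopsy before treatment and, if done, one at 2 weeks. For the other lesion it says only: "Additionally, when available, a non-treated tumor will be biopsied two weeks after treatment to assess for immune cell infiltration". In Section 7.4 the pre-RE biopsy is of the largest accessible tumour that is to be treated. The other lesion enters only under the optional post-RE biopsy, as a "non-treated lesion (defined as a lesion which did not receive y90 as determined on standard of care Bremsstrahlung scan after RE"). Section 7.4 closes the topic with: "The infiltration of immune cells into the tumor before and after treatment will then be compared with each patient serving as their own control".

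**Sampling elsewhere.** The biopsy row of the Section 7.2 calendar has an unqualified X before RE and names "a treated and an untreated tumor" only in the 2-week column. The synopsis says that tumour areas outside the initial treatment site are biopsied too, but gives no time for it.

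**The concern.** A paired test of change needs two values from the same unit, one before and one after. The sections that tell staff what to collect give the non-treated tumour only the second value. Its non-treated status is also fixed by a scan done after RE, and no rule links a pre-RE sample to a lesion later classed that way.

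Two consequences follow. The direct one is that the secondary objective cannot be met as the analysis is written. The indirect one is that someone may fill the gap at analysis. Section 7.4 makes the patient, not the lesion, the control, and Section 10 does not say which baseline belongs to which lesion. Pairing the post-RE non-treated lesion with the pre-RE treated lesion would be a within-patient pair but a between-lesion contrast, and any standing difference between the two lesions would be read as change over time.

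This matters for interpretation because Section 2 gives the abscopal effect as a reason for studying RE, and the non-treated tumours are the only tumour tissue outside the treated site that the study samples.

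**Working it through.** **Step 1: count the scheduled pairs.** The documents give no power, effect size, standard deviation or expected number of biopsy pairs, so there is no plan figure to reproduce. The check is to list the biopsy times by lesion.

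| Source | Treated tumour | Non-treated tumour |
|---|---|---|
| Synopsis | before RE; optional at 2 weeks | biopsied, time not stated |
| 7.2 calendar | pre-RE X names no lesion; 2 weeks, optional | pre-RE X names no lesion; 2 weeks, optional |
| 7.3 | before RE; 2 weeks if done | 2 weeks, when available |
| 7.4 | before RE; optional at 2 weeks | optional at 2 weeks |
| Section 10 | paired test of change | paired test of change |

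Scheduled same-lesion pairs under 7.3 and 7.4, for the accrual goal of 30:

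- Treated: 1 per patient who has the optional biopsy, so 0 to 30.
- Non-treated: 0 per patient, so 0 of 30.

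If the synopsis is read as including a pre-RE biopsy of the other areas, the non-treated count becomes 0 to 30. It then depends on how many patients have such a lesion and accept the optional biopsy. The documents give neither proportion.

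**Step 2: how many post-RE non-treated samples might there be (assumed inputs).** Number = 30 × acceptance × availability, with each proportion taken as 0.25 to 0.75:

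- 30 × 0.25 × 0.25 = 1.9
- 30 × 0.50 × 0.50 = 7.5
- 30 × 0.75 × 0.75 = 16.9

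**Step 3: what a borrowed baseline would do (illustration, assumed inputs).** Suppose there is no true change, the two lesions differ on average by b standard deviations, and values from two lesions in one patient correlate at rho. The standardised mean of the paired differences is b / sqrt(2(1 − rho)). Multiplied by sqrt(n), this is the noncentrality of the paired t-test on n − 1 degrees of freedom. The two-sided level is 0.05, from Section 10.

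Worked case: b = 0.5, rho = 0.5, n = 15. The standardised difference is 0.5 / sqrt(1) = 0.5, the noncentrality is 0.5 × sqrt(15) = 1.94, and the rejection probability is 43.8%. Simulation with 200,000 trials gave 44.0%.

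Rejection probability (%) at rho = 0.3 / 0.5 / 0.7:

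| b (SD) | n = 15 | n = 7 |
|---|---|---|
| 0 | 5.0 | 5.0 |
| 0.1 | 6.1 / 6.5 / 7.5 | 5.4 / 5.6 / 6.0 |
| 0.3 | 15.0 / 19.2 / 28.7 | 8.8 / 10.3 / 14.0 |
| 0.5 | 33.2 / 43.8 / 64.3 | 15.7 / 20.1 / 30.2 |

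With only 2 pairs and b = 0.5, the rates are 5.9 / 6.2 / 6.9. The inflation therefore needs both a systematic lesion difference and a workable number of pairs.

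**The case against.** The best counter-argument is that the synopsis does supply a baseline. Its sentence about other tumour areas follows directly on one naming both the pre-RE and the 2-week biopsy, so both times may carry over. Whether an area lies outside the treatment site could be judged from the mapping angiogram, with the later scan only confirming it. On that reading the paired test is coherent and 7.3 and 7.4 are merely incomplete. This reading is possible, but it does not remove the problem: the detailed sections would then omit a required sample, and the passages would still need reconciling.

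The zero is a count of scheduled pairs, not a proof that no pair can arise. A lesion biopsied before RE as one to be treated could show no y90 on the later scan, be classed as non-treated and be biopsied again. That would be incidental, and the plan does not provide for it.

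It is also fair that no passage proposes borrowing another lesion's baseline and that the rejection rates rest on assumed inputs. They show what the gap permits; the finding does not depend on them.

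Finally, 7.2 and 7.4 do not state outright that the treated lesion sampled after RE is the one sampled before. The synopsis, 7.3 and the opening of the biopsy paragraph in 7.4 do describe one treated tumour before and after, so I do not extend the point to that comparison.

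**Conclusion.** The point holds and should be fixed. Under Sections 7.3 and 7.4 as written, the Section 10 paired test in non-treated tumours has 0 scheduled same-lesion pairs among 30 patients, and the secondary objective of change cannot be estimated. This rests on the text alone. The synopsis and the calendar neither schedule nor clearly exclude a baseline.

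The risk of a false claim of change is conditional. It arises only if a different lesion's baseline is used and the lesions differ systematically. Under the assumed correlations, the nominal 5% error rises to 9 to 14% with 7 pairs and 15 to 29% with 15 pairs at a 0.3 SD difference; at no difference it stays at 5%.

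The primary peripheral-blood analysis and the treated-tumour comparison are not affected.

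**What to change.** 1. **Reconcile the schedule.** State in the synopsis and in 7.2 to 7.4 whether tumour areas outside the treatment site are sampled before RE, after RE or both, and name the lesion in the pre-RE calendar cell. Which of these is right is for the sponsor to settle.
2. **Define the paired set in Section 10.** Suggested wording: *The paired pre/post test in non-treated tumours includes only patients with a pre-RE sample of that same lesion, confirmed as non-treated on the post-RE scan; a baseline from another lesion is not used. The number of pairs is reported.*
3. **Where no such sample exists,** restate the objective and the analysis as a post-RE description plus a within-patient treated-minus-non-treated difference at 2 weeks. Label it a difference between lesions, not change and not evidence of an abscopal effect: an effect shared by both lesions cancels out of it, and baseline differences between them remain in it.

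The cost is wording in the synopsis, 7.2 to 7.4, the objective and Section 10. These changes do not themselves add a biopsy, which matters because Section 7.3 records that "The second biopsy was made optional as it was found to be a significant barrier to enrollment". The real loss is scientific: without a same-lesion baseline the trial gives up the claim of change in non-treated tumours, and the replacement contrast cannot by itself show a systemic effect.

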- Determine changes in the peripheral blood cytokines after radioembolization (RE) therapy for primary and secondary malignancies of the liver.
- Determine the changes in infiltrating immune cells within the treated tumor, which occur after RE therapy for primary and secondary malignancies of the liver.

- Determine the changes in infiltrating immune cells within non-treated liver tumors, which occur after RE therapy for primary and secondary malignancies of the liver.
- Determine changes in the peripheral blood lymphocytes after RE therapy for primary and secondary malignancies of the liver at 7 days, 4 weeks, and 12 weeks.

Key Inclusion Criteria:

- Biopsy or image (in the setting of hepatocellular carcinoma (HCC)) diagnosed hepatic malignancy
- Total bilirubin < 2 mg/dL
- ECOG status ≤ 2
- Life expectancy >3 months assessed
- Age >22 years
- Lesion >2.0 cm which is amenable to percutaneously biopsied

Key Exclusion Criteria:

- Unwilling or unable to attend all study related follow ups
- Technetium 99 macro aggregated albumin (MAA) lung shunt fraction >20%
- Arterial anatomy which precludes the ability to safely perform RE
- INR > 3 or platelet count <15,000 which cannot be corrected
- Patients who are unable to hold anticoagulation and/or antiplatelet therapy in the peri-procedural setting

Accrual Objective:

The goal is to accrue 30 patients. It is anticipated that approximately 10 patients per year can be enrolled; meaning enrollment is expected to take 60 months.

1 Objectives

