3.1 Inclusion Criteria

- 3.1.1 Diagnosis of primary hepatocellular carcinoma or biopsy proven hepatic metastases from another solid tumor primary for which RE is planned
- 3.1.2 Hepatic lesion >2.0 cm which is amenable to percutaneously biopsy

- 3.1.3 Age 22 years or older
- 3.1.4 EOCG PS ≤ 2 – refer to Appendix II
- 3.1.5 Total bilirubin ≤ 2.0 mg/dL
- 3.1.6 Expected life expectancy of >3 months assessed
- 3.1.7 Participant provides voluntary written consent prior to the performance of any research related tests or procedures

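### Section 7.4 defines progression free survival by progression alone, so a death without documented progression is not an event; this is time to progression under the PFS name

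*Combined protocol and SAP*

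**What the plan says.** Section 7.4 holds all the relevant definitions.

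- Imaging: "Clinical follow up with magnetic resonance imaging (MRI) or CT will occur at 1 month and 3 months".
- Response: "Radiologic response will be evaluated at 3 months using Response Evaluation Criteria in Solid Tumors (RECIST) and modified RECIST guidelines".
- Overall survival: "Overall survival will be defined as time from RE to death, and patients will be censored for transplantation".
- PFS: "Progression free survival will be defined as time from RE to progression as defined by RECIST and mRECIST".

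The overall survival sentence comes directly before the PFS sentence. It is the only place where death is a time-to-event outcome. Its transplantation rule is attached to overall survival and is not repeated for PFS.

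PFS does not appear among the objectives (Synopsis and Section 1) or the endpoints (Section 7.3). Section 10 describes analyses of lymphocytes, cytokines and tumour infiltration. It contains no time-to-event method and no censoring rule for PFS.

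**The concern.** PFS is ordinarily understood to end at progression or death, whichever comes first. Under the Section 7.4 definition, a patient who dies before a scan shows progression never has an event. That patient has one of the worst outcomes in the cohort, yet would count as progression-free up to death or be left out of the count.

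This is a rule that is wrong as written, not a missing detail. Someone who follows it exactly obtains time to progression and reports it as PFS. The result could not be compared with PFS from studies that count deaths, and where the two differ the difference would flatter this cohort.

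Such deaths are conceivable in this population. Section 3.1 admits patients with "Expected life expectancy of >3 months assessed", and Section 5 foresees that participation may end early because "The patient is discharged to hospice for terminal cancer care". Section 7.4 names scans at only two times, so a patient can deteriorate and die between them without progression being documented.

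**Working it through.** **Plan's own figure.** None. The documents give no PFS rate, median, event count or survival method, so there is nothing to reproduce.

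**Step 1: what counts as an event.** The two adjacent definitions in Section 7.4 compare as follows.

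| Outcome | Starts | Event | Censoring stated |
|---|---|---|---|
| Overall survival | RE | Death | Transplantation |
| PFS | RE | Progression only | None |

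No other section adds death to the second row.

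**Step 2: direction.** Let P be the proportion who progress first and D the proportion who die without documented progression by a fixed time, with complete follow-up to that time. PFS with deaths counted is 1 − P − D. The plan does not say how such deaths would be handled, so take the three obvious ways in turn.

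- Left as event-free: the estimate is 1 − P, which is at least 1 − P − D.
- Removed from the denominator: (1 − P − D)/(1 − D), which is at least 1 − P − D.
- Censored at the date of death in a Kaplan-Meier estimate: each step caused by a death is replaced by a factor of 1 and the other steps are unchanged, so the curve is equal or higher.

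All three agree in direction. They give no overstatement when D = 0.

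**Step 3: size, by assumption.** Assume independent constant hazards, λp for progression and λd for death without progression, with deaths censored.

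- Rule as written at 3 months: exp(−3λp).
- PFS with deaths counted: exp(−3(λp + λd)) = exp(−3λp) × (1 − d), where d = 1 − exp(−3λd) is the assumed 3-month risk of death without progression.
- With a median time to progression of 6 months, λp = ln 2/6 and exp(−3λp) = 0.707.

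| Assumed d | Rule as written | Deaths counted | Overstatement (points) |
|---|---|---|---|
| 0% | 70.7% | 70.7% | 0 |
| 5% | 70.7% | 67.2% | 3.5 |
| 10% | 70.7% | 63.6% | 7.1 |
| 20% | 70.7% | 56.6% | 14.1 |

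The overstatement equals exp(−3λp) × d. For a median of 4 months, exp(−3λp) = 0.595; for 9 months it is 0.794. Over medians of 4 to 9 months and d from 5% to 20%, the overstatement runs from 0.595 × 0.05 = 3.0 points to 0.794 × 0.20 = 15.9 points.

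**Step 4: would it arise in this cohort?** The Synopsis states: "The goal is to accrue 30 patients". If each patient has probability p of dying without documented progression, the chance of at least one such death is 1 − (1 − p)^30.

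| Assumed p | Expected deaths (30p) | Chance of at least one |
|---|---|---|
| 1% | 0.3 | 26% |
| 5% | 1.5 | 79% |
| 10% | 3 | 96% |
| 20% | 6 | 99.9% |

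Here p is the proportion actually observed to die first. It is a separate assumption from d in Step 3.

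**The case against.** The strongest reply is that little depends on this sentence. PFS is not an objective or endpoint, no analysis of it is planned, and no PFS censoring rule or Kaplan-Meier estimate is written down. The figures above therefore come from assumed rates and an assumed estimator. Entry also requires a life expectancy above three months, so early deaths without progression may be few or none. All of this stands, and it limits the importance of the point. It does not make the definition correct, because Step 2 does not depend on the estimator chosen.

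Four stronger readings are tempting, and the documents do not support them.

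- **PFS will be overstated.** This needs at least one death without documented progression. The documents give no rate, and zero is possible.
- **Each patient has two conflicting progression dates.** Naming RECIST and mRECIST together can be read as one result per criterion, in line with the response sentence, which also names both. The wording should be clarified, but it is not a demonstrated error. Nothing in the documents ranks one criterion above the other.
- **The 3-month scan is lost because participation ends early.** Section 5 says "Direct study participation ends after the final blood sample is collected 12 weeks after the RE therapy", and the ±2-week window allows that sample from day 84 − 14 = 70, before a scan at about day 91. But Section 7.4 describes the scans as clinical follow-up, and they are not in the research sampling schedule. An early last blood draw does not stop them, and nothing bars their use.
- **Correlations of immune change with PFS would be biased.** No such correlation is planned.

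**Conclusion.** The point holds as a definitional error of limited reach. The protocol defines time to progression and calls it PFS. Any deaths without documented progression would make the reported figure equal to or higher than PFS with deaths counted. The direction follows from the definition; the size cannot be derived from the documents. Under constant independent hazards and a 6-month median time to progression, it is about 0, 3.5, 7 or 14 points at 3 months for a 0%, 5%, 10% or 20% risk of such death. The primary analysis, the secondary analyses and the accrual goal of 30 do not depend on it.

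**What to change.** In Section 7.4, do one of the following:

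- define PFS as time from RE to the first of progression or death from any cause, with patients who have neither censored at their last evaluable scan; or
- keep the present event and rename the quantity time to progression.

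As a clarification in the same place, state that RECIST and mRECIST give two separate results, each reported under its own name.

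The cost is one or two sentences. No extra patients, visits, scans or samples are needed. If deaths without progression occur and the first option is taken, reported PFS will be lower than under the present wording.
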